- c. Serum Creatinine (Cr) Interpretation
 - ii. Is Cr >20% higher than value prior to initiation or last increase of ACEi/ARB?
 - 1. Yes. Discuss with provider decreasing dose by 50% (or stopping if at starting dose). Discuss follow up plan for Cr with provider as well.
 - 2. No
 - (i) Is creatinine within 30% of baseline since initiation?
 - (a) No. Discuss with provider decreasing dose by 50% (or stopping if at starting dose). Discuss follow up plan for Cr with provider as well.
 - (b) Yes. Proceed to RN BP Assessment.
 - 3. RN BP Assessment
 - a. Perform RN BP Assessment as detailed above.
 - b. Is BP at goal based on definitions above?
 - i. Yes. Continue regimen and schedule RN BP Assessment Visit in 3 months and follow-up with PCP within 6 months.
 - 1. If BP continues to be at goal in 3 months, this protocol is COMPLETE and can return hypertension management to PCP.
 - ii. No
 - 2. Is ACEi/ARB at maximum tolerated dose?
 - (i) Yes. This protocol is COMPLETE. Initiate NON-ACEi/ARB PROTOCOL.
 - (ii) No route pended order to provider for double prior dose of current ACE and return to "Follow-Up" above.

NON ACEi/ARB PROTOCOL

- 1. Discuss with provider selection of next anti-hypertensive protocol.
- 2. Discuss following medication suggestions with provider. These are only suggestions to guide management, but final selection is at provider's discretion.
 - a. If patient has history of myocardial infarction or heart failure, recommend BETA-BLOCKER PROTOCOL.
 - i. Recommend carvedilol given dual properties of heart rate reduction (beta blockade) and vasodilation (alpha blockade) and, therefore, typically greater impact on blood pressure.
 - ii. Recommended starting dose: carvedilol 6.25mg twice daily.
 - iii. Maximum dose: carvedilol 25mg twice daily.
 - iv. Class-specific considerations
 - 1. Low heart rate (bradycardia)
 - 2. Lower extremity swelling, erectile dysfunction, fatigue.
 - 3. Exacerbation of asthma or chronic obstructive lung disease symptoms (shortness of breath or wheezing).
 - b. If patient is on maximum tolerated beta-blocker or has no history of myocardial infarction or heart failure, recommend DIURETIC PROTOCOL.
 - i. For patients with GFR > 30 mL/min, recommend chlorthalidone.
 - 1. Starting dose 12.5mg once daily.
 - 2. Maximum dose 25mg once daily. However, dose adjustment is dependent on provider assessment of volume status. All follow-up

evaluations should be discussed with provider.

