- ii. For patients with GFR < 30, recommend furosemide.
 - 1. Starting dose 20mg twice daily.
 - a. Maximum dose dependent on provider assessment of volume status. All follow-up evaluations should be discussed with provider.
- iii. Class-specific considerations
 - 1. Must counsel patients that diuretics will increase urinary frequency
 - 2. May worsen prostate symptoms in men.
- c. If patient is already on maximum tolerated diuretic and no history of myocardial infarction or heart failure, recommend CALCIUM CHANNEL BLOCKER PROTOCOL.
 - i. For patients with proteinuria, recommend non-dihydropyridine calcium channel blocker (CCB) verapamil SR as it may help reduce proteinuria.
 - 1. Recommended starting dose verapamil SR 120mg once daily.
 - 2. Maximum dose verapamil SR 360mg once daily.
 - ii. For patients without proteinuria, dihydropyridine CCB amlodipine may be used.
 - 1. Recommended starting dose amlodipine 5mg once daily.
 - 2. Maximum dose amlodipine 10mg once daily.
 - iii. Class-specific considerations
 - 1. Amlodipine may cause increased heart rate (reflex tachycardia).
 - 2. Verapamil may cause bradycardia and constipation.

Both may cause lower extremity swelling.
- d. If patient is already on maximum tolerated doses of beta-blocker, diuretic and calcium channel blocker, recommend HYDRALAZINE PROTOCOL.
 - i. Hydralazine
 - 1. Recommended starting dose 10mg three times daily.
 - 2. Maximum dose 100mg three times daily.
 - iii. Class-specific considerations
 - 1. May cause reflex tachycardia.
- e. If patient is already on maximum tolerated doses of beta-blocker, diuretic and calcium channel blocker and hydralazine, discuss with provider the following:
 - i. Referral to Hypertension Clinic.
 - ii. Referral to clinical pharmacist for full medication review and assessment of adherence.
 - iii. Return management of hypertension to PCP for work-up of secondary hypertension and selection of fifth anti-hypertensive agent.

BETA-BLOCKER PROTOCOL

1. Discuss following medication suggestions with provider. These are only suggestions to guide management, but final selection is at provider's discretion.
2. Perform RN BP Assessment as detailed above.
3. Is BP at goal?
 - a. Yes. Continue regimen and schedule RN BP Assessment Visit in 3 months and follow-up with PCP within 6 months.
 - i. If BP continues to be at goal in 3 months, can return hypertension management to PCP.

- b. No 4 is HR > 60?

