 - i. Yes. Route pended order to provider for carvedilol 6.25mg twice daily (or alternative beta-blocker as directed by provider) and schedule for "Follow-Up" as detailed below in 2-4 weeks.
 - ii. No. Discuss with provider safety of starting beta-blocker or alternatively selection of diuretic, calcium channel blocker or hydralazine protocols.
- 4. Follow-Up
 - a. Perform RN BP Assessment as detailed above in 2-4 weeks.
 - b. Is BP at goal?
 - i. Yes. Continue regimen and schedule RN **BP** Assessment Visit in 3 months and follow-up with PCP within 6 months.
 - 1. If BP continues to be at goal in 3 months, can return hypertension management to PCP.
 - ii. No. Is HR > 60?
 - 1. Yes. Is beta-blocker at maximum dose?
 - a. No. Route pended order to provider for double prior dose of beta-blocker and schedule for "Follow-Up" as detailed above in 2-4 weeks.
 - b. Yes. Return to NON-ACEi/ARB PROTOCOL for selection of next medication.
 - 2. No. Discuss with provider safety of continuing beta-blocker or selection of diuretic, calcium channel blocker or hydralazine protocols.

DIURETIC PROTOCOL

- 1. Discuss following medication suggestions with provider. These are only suggestions to guide management, but final selection is at provider's discretion.
- 2. Perform RN BP Assessment as detailed above.
- 3. Is BP at goal?
 - a. Yes. Continue regimen and schedule RN BP Assessment Visit in 3 months and follow-up with PCP within 6 months.
 - i. If BP continues to be at goal in 3 months, can return hypertension management to PCP.
 - b. No. Proceed with diuretic selection
- 4. Diuretic selection
 - a. If no K or GFR in last three months then order POTASSIUM LEVEL and CREATININE WITH eGFR in EHR.
 - i. Is K > 3.5?
 - 1. No. Discuss with provider safety of initiation or titration of diuretic or need for potassium supplementation and schedule for "Follow-Up" as detailed below in 2-4 weeks after provider has provided recommendation.
 - 2. Yes. Is patient already taking diuretic?
 - a. Yes. Discuss with provider next choice (consider recommendations below based on GFR) and schedule for "Follow-Up" as detailed below in 2-4 weeks.

- b. No. Is GFR > 30?
 - (i) Yes. Recommend thiazide diuretic such as chlorthalidone 12.5mg or other diuretic selected by provider and schedule for "Follow-Up" as detailed below in 2-4 weeks.
 - (ii) No. Recommend furosemide 20mg twice daily or other diuretic selected by provider and schedule for "Follow-Up" as detailed below in 2-4 weeks.

5. Follow-Up

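### Step 3b of the Appendix I beta-blocker protocol has no branch for current users, so read literally its suggested order leaves carvedilol 6.25 mg unchanged and halves 12.5 mg

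*Combined protocol and SAP*

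**What the plan says.** All of the relevant text is in Appendix I, the hypertension management protocol, which an RN carries out.

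**Entry.** NON ACEi/ARB PROTOCOL, item 2a: "If patient has history of myocardial infarction or heart failure, recommend BETA-BLOCKER PROTOCOL". Item 2b gives the exit: "If patient is on maximum tolerated beta-blocker or has no history of myocardial infarction or heart failure, recommend DIURETIC PROTOCOL". Item 2a also fixes the dose range: "Recommended starting dose: carvedilol 6.25mg twice daily" and "Maximum dose: carvedilol 25mg twice daily".

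**Step 3b of the BETA-BLOCKER PROTOCOL.** When blood pressure is not at goal, the one question is whether heart rate is above 60. If it is: "Yes. Route pended order to provider for carvedilol 6.25mg twice daily (or alternative beta-blocker as directed by provider", with Follow-Up to be scheduled in 2-4 weeks. If it is not, the RN discusses with the provider whether starting the drug is safe, or chooses another class.

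**Follow-Up (step 4).** Item 4a: "Perform RN BP Assessment as detailed above in 2-4 weeks". If blood pressure is still above goal, item 4b(ii) checks heart rate, then whether the dose is at maximum. Below maximum, it pends a doubling.

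**Safeguards.** NON ACEi/ARB item 1 reads "Discuss with provider selection of next anti-hypertensive protocol". Step 1 of the BETA-BLOCKER PROTOCOL says "These are only suggestions to guide management, but final selection is at" the provider's discretion. The introduction to Appendix I leaves drug and dose to the provider and lets a PA or NP suggest deviations. Section 7.2 makes activation of the study protocol optional for the practitioner. The RN BP ASSESSMENT, which step 2 calls for, includes asking the patient about every blood-pressure drug.

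**The concern.** Item 2b names the maximum tolerated dose as a reason to leave for the diuretic protocol, so the appendix expects some patients to arrive already on a beta-blocker. Those below maximum stay in the beta-blocker protocol, yet step 3b treats everyone as a new starter. Its low-heart-rate branch speaks of starting the drug, whereas the matching Follow-Up branch speaks of continuing it.

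What is at stake is the default order put in front of the provider. For a patient on carvedilol 6.25 mg or 12.5 mg twice daily whose blood pressure is too high, that default keeps or lowers the dose, where the appendix's own titration rule would raise it.

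**Working it through.** The plan states no figure to reproduce. The check traces the algorithm and applies its stated doses.

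**1. Can a current user reach step 3b?** Item 2a conditions only on previous MI or heart failure. Item 2b removes those on the maximum tolerated beta-blocker. A patient with that history on a lower dose meets 2a and is not removed by 2b. So yes.

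**2. Does step 3b use current dose?** No. Its only branch is on heart rate. The dose check and the doubling appear only in Follow-Up 4b(ii), and no line in step 3b sends an existing user there.

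**3. How do the other drug protocols in Appendix I treat current users at the same point?**

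| Protocol | Current user, blood pressure above goal |
|---|---|
| ACEi/ARB | Dose increase if below maximum tolerated |
| Calcium channel blocker | Asks about current use; doubles if below maximum |
| Hydralazine | 10 mg goes to 25 mg; 25 mg or more is doubled if below maximum |
| Diuretic | Asks about current use; refers to the provider |
| Beta-blocker, step 3b | No question on current use; starting dose pended |

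**4. Size of the pended order.** Let d be the current carvedilol dose in mg twice daily. Inputs from item 2a: start 6.25, maximum 25. With blood pressure above goal and heart rate above 60, the step 3b order relative to the current dose is 6.25/d. The Follow-Up rule gives 2d/d = 2.

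- d = 6.25: step 3b pends 6.25, ratio 6.25/6.25 = 1.0. Follow-Up would pend 2 × 6.25 = 12.5.
- d = 12.5: step 3b pends 6.25, ratio 6.25/12.5 = 0.5. Follow-Up would pend 2 × 12.5 = 25, the stated maximum.
- d below 6.25: the ratio exceeds 1, so step 3b raises the dose. These patients are not affected in this way.

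**5. Delay to the first order above the current dose.** Assume that every pended order is accepted unchanged, blood pressure stays above goal, heart rate stays above 60, visits keep the 2-4 week interval, and the dose has been unchanged for at least 2 weeks at entry, so that doubling at entry is the fair comparison.

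- d = 6.25: literal sequence 6.25, 12.5, 25; titration sequence 12.5, 25. The first increase comes at the next visit instead of at entry: 1 × (2-4) = 2-4 weeks.
- d = 12.5: literal sequence 6.25, 12.5, 25; titration sequence 25. The first increase comes two visits later: 2 × (2-4) = 4-8 weeks.

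These are upper ends. If the provider corrects the order in the discussion before step 3, the delay is 0. The ranges are therefore 0 to 2-4 weeks and 0 to 4-8 weeks. Other doses were not traced for delay.

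**The case against.** The strongest reply is that step 3b is evidently the initiation step and Follow-Up the titration step, as the contrast between starting and continuing shows. The RN has just asked about each blood-pressure drug. The provider has been consulted under NON ACEi/ARB items 1 and 2 and again under step 1, and must still sign the order. For a dose to be cut, an RN who knows the patient takes 12.5 mg must pend half of it, and a provider must accept that.

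Most of this stands, and it is why the point is minor. It also shows that the information is already in hand and only the branch is missing. It does not supply that branch. The same provider-discretion sentence opens the diuretic, calcium channel blocker and hydralazine protocols, and those still branch on current use. The appendix gives no reason for treating beta-blockers differently.

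Two further objections have some force. The heart-rate line of step 3b carries a stray digit in the text as read, possibly from conversion, so it should be checked against the source layout. The surrounding branches read as complete, however. Also, a branch that sent every carvedilol user straight to doubling would lose the 2-4 week interval built into Follow-Up. The fix has to keep that interval.

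A reader might infer more than the documents support:

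- **That patients will have their dose halved.** The figures describe pended orders, not doses taken.
- **That users of another beta-blocker will be given two.** The text does not say whether carvedilol would replace or be added to the existing drug, and it allows an alternative chosen by the provider.
- **That the trial comparison is affected.** Nothing in the documents links this step to the hospitalization result, and the number of patients concerned is not given.

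**Conclusion.** The point holds as a drafting gap with a small patient-safety consequence. A nurse-run rule, read literally, produces a suggested order that conflicts with the appendix's own titration rule: 1.0 times the current dose at 6.25 mg and 0.5 times at 12.5 mg, against 2.0 times under Follow-Up 4b(ii). This is confined to patients with previous MI or heart failure who take submaximal carvedilol, with blood pressure above goal and heart rate above 60. Provider selection limits the harm but does not correct the order as written. Sample size, error rates and the primary analysis are not touched.

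**What to change.** Before the heart-rate question in step 3b, ask whether the patient already takes a beta-blocker, with these routes:

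1. **Carvedilol, dose unchanged for at least 2 weeks:** go to Follow-Up 4b(ii), that is, the heart-rate check, the maximum-dose check, then a doubling or return to the NON ACEi/ARB PROTOCOL.
2. **Carvedilol, started or changed within the last 2 weeks:** schedule Follow-Up for 2-4 weeks after that change.
3. **Another beta-blocker:** discuss titration or a switch with the provider before pending any order, because Appendix I states a maximum dose only for carvedilol.
4. **None:** continue with the existing heart-rate question and starting order.

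The RN already asks about current drugs, so the only added detail is the date of the last carvedilol change. The cost is a short amendment, the same edit in any smart set that carries the step, and approval by all the IRBs under section 14.2. It can be made at the appendix's yearly review. The downside is that the suggested order at entry becomes a doubling for stable submaximal carvedilol users with MI or heart failure. That follows the appendix's existing titration rule and still goes to the provider for selection.

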
- a. Schedule RN BP Assessment Visit in 2-4 weeks
- b. Order POTASSIUM LEVEL and CREATININE WITH E-GFR and request patient have labs drawn at least 1 business day prior to visit.
- c. Perform RN BP Assessment as detailed above in 2-4 weeks.
- d. Is K > 3.4?
 - i. No. Discuss with provider change in therapy or potassium supplementation. Discuss follow up plan for K with provider as well.
 - ii. Yes
 - 1. Is GFR > 10% lower than last value?
 - a Yes. Discuss with provider decrease in diuretic dose or stopping diuretic. Discuss follow up plan for Cr with provider as well.
 - b No. Is BP at goal?
 - (i) If BP is still not at goal at maximum tolerated dose of diuretic, return to NON-ACEi/ARB PROTOCOL.
 - (ii) If BP is still not at goal and not taking chlorthalidone 25mg or maximum tolerated dose of diuretic, then discuss with provider if dose of diuretic should be increased.
 - (iii) If provider recommends to increase dose, schedule for "Follow-Up" as detailed above in 2-4 weeks.
 - (iv) If provider recommends to not increase dose, return to NON-ACEi/ARB PROTOCOL.

CALCIUM CHANNEL BLOCKER PROTOCOL

1. Discuss following medication suggestions with provider. These are only suggestions to guide management, but final selection is at provider's discretion.
2. Perform RN BP Assessment as detailed above.
3. Is BP at goal?
 - a. Yes. Continue regimen and schedule RN BP Assessment Visit in 3 months and follow-up with PCP within 6 months.
 - i. If BP continues to be at goal in 3 months, can return hypertension management to PCP.
 - b. No. Is patient already taking calcium channel blocker (CCB)?
 - i. Yes - Is CCB at maximum dose?
 - 1 Yes. Return to NON-ACEi/ARB PROTOCOL.
 - 2 No. Route pended order to provider for double dose of current CCB and schedule for "Follow-Up" as detailed below in 2-4 weeks.
 - a No. Does patient have proteinuria as defined above?
 - b Yes. Route pended order for verapamil SR 120mg once daily and

proceed to "Follow-Up" below.

c No. Route pended order for amlodipine 5mg once daily and schedule for "Follow-Up" as detailed below in 2-4 weeks.

4. Follow-Up

- Perform RN BP Assessment as detailed above in 2-4 weeks.
- Is HR ≥ 100 ?
 - Yes - discuss with provider
 - No. Is BP at goal?
 - Yes. Continue regimen and schedule RN BP Assessment Visit in 3 months and follow-up with PCP within 6 months.
 - If BP continues to be at goal in 3 months, can return hypertension management to PCP.
 - No. Is CCB at maximum dose?

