 - No. Route pended order to provider for double dose of current CCB and return to follow-up above.
 - Yes. Return to NON-ACE i/ARB PROTOCOL.

HYDRALAZINE PROTOCOL

- Discuss following medication suggestions with provider. These are only suggestions to guide management, but final selection is at provider's discretion.
- Perform RN BP Assessment as detailed above.
- Is BP at goal?
 - Yes. Continue regimen and schedule RN BP Assessment Visit in 3 months and follow-up with PCP within 6 months.
 - If BP continues to be at goal in 3 months, can return hypertension management to PCP.
 - No. Route pended order to provider for hydralazine 10mg PO TID. If patient is already taking hydralazine 10mg PO TID, route pended order to provider for dose to 25mg PO TID. If patient is already taking 25mg or more TID, route pended order to provider for double current dose of hydralazine if not at maximum dose. Schedule for "Follow-Up" as detailed below in 2-4 weeks.
- Follow-Up
 - Perform RN BP Assessment as detailed above in 2-4 weeks.
 - is HR > 100 ?
 - Yes. Discuss with provider
 - No. Is BP at goal?
 - Yes. Continue regimen and schedule RN BP Assessment Visit in 3 months and follow-up with PCP within 6 months.
 - If BP continues to be at goal in 3 months, can return hypertension management to PCP.
 - No. Is hydralazine at maximum dose?
 - No. Route pended order to provider for double current dose of hydralazine and return to follow-up above.
 - Yes. Return to NON-ACEi/ARB PROTOCOL.

References

James PA et al. 2014 Evidence-based Guideline for the Management of High Blood Pressure in Adults. Report from the Panel Members Appointed to the Eighth Joint National Committee (JNC 8). *JAMA* 2014, 311(5):507-520

Kidney Disease: Improving Global Outcomes (KDIGO) CKD Work Group. KDIGO 2012 Clinical Practice Guideline for the Evaluation and Management of Chronic Kidney Disease. *Kidney International* 2013, Supp 3:1-150

Kidney Disease: Improving Global Outcomes (KDIGO) Blood Pressure Work Group. KDIGO Clinical Practice Guideline for the Management of Blood Pressure in Chronic Kidney Disease. *Kidney International* 2012, Supp 2:337-414

K/DOQI Clinical Practice Guidelines for Chronic Kidney Disease: Evaluation, Classification and Stratification. *Am J Kidney Dis* 2002, 39: S266.

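### Followed literally from their stated starting doses, two Appendix I titration loops propose orders above the appendix's own maxima: verapamil SR 480 mg against 360 mg once daily, and hydralazine 160 mg against 100 mg three times daily

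*Combined protocol and SAP*

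**What the plan says.** The dose limits are in Appendix I, NON ACEi/ARB PROTOCOL, items 2c and 2d. For verapamil SR the appendix gives "Recommended starting dose verapamil SR 120mg once daily" and "Maximum dose verapamil SR 360mg once daily". Hydralazine starts at 10 mg three times daily, with a maximum of 100 mg three times daily.

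The titration rules come later in the same appendix.

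- **CALCIUM CHANNEL BLOCKER PROTOCOL, item 3.** For a patient already on such a drug and above goal, the nurse asks "Is CCB at maximum dose". If the answer is no, the instruction is "Route pended order to provider for double dose of current CCB".
- **The same protocol, item 4 (Follow-Up).** The same question is asked. If the answer is no, the instruction is "Route pended order to provider for double dose of current CCB and return to follow-up above".
- **HYDRALAZINE PROTOCOL, item 3b.** This item has its own first step: "If patient is already taking hydralazine 10mg PO TID, route pended order to provider for dose to 25mg PO TID". From 25 mg three times daily upward it doubles unless the drug is already at maximum.
- **The same protocol, item 4 (Follow-Up).** The nurse asks "Is hydralazine at maximum dose". If the answer is no, the instruction is "Route pended order to provider for double current dose of hydralazine and return to follow-up above".

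The introduction to Appendix I leaves the final choice of drug and dose to the provider. Item 1 of each of these protocols calls its medication steps suggestions. Section 6.5 makes use of the protocols optional for the practitioner.

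**The concern.** Each doubling line tests the dose the patient is taking now, not the dose about to be proposed. That is harmless when the maximum is the starting dose times a power of two. It fails otherwise, because the last doubling jumps over the limit. Verapamil SR (360/120 = 3) and hydralazine (100/10 = 10) are the two cases where the ratio is not a power of two.

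A nurse applying the lines as printed could therefore send the provider a draft order above the limit printed earlier in the same appendix. Verapamil SR is also the agent the appendix recommends, within this class, for patients with proteinuria, and albuminuria or proteinuria is one of the two routes to CKD eligibility in section 5.1.1. The hydralazine follow-up raises a second issue: it gives a different next dose from item 3b for the same patient on 10 mg three times daily.

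**Working it through.** **Inputs.** Starting and maximum doses are from Appendix I: the Goals/Background list for lisinopril and losartan, and the NON ACEi/ARB PROTOCOL for the rest. The interval between steps, 2 to 4 weeks, is from the follow-up items of the calcium channel blocker and hydralazine protocols.

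**Rule as written.** While the current dose d is below the maximum M, the next proposed dose is 2d.

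| Drug | Start | Maximum | Doses under the rule | Last dose / maximum |
|---|---|---|---|---|
| Lisinopril, once daily | 5 mg | 40 mg | 5-10-20-40 | 1.00 |
| Lisinopril, low start | 2.5 mg | 40 mg | 2.5-5-10-20-40 | 1.00 |
| Losartan, once daily | 25 mg | 100 mg | 25-50-100 | 1.00 |
| Carvedilol, twice daily | 6.25 mg | 25 mg | 6.25-12.5-25 | 1.00 |
| Amlodipine, once daily | 5 mg | 10 mg | 5-10 | 1.00 |
| Verapamil SR, once daily | 120 mg | 360 mg | 120-240-480 | 480/360 = 1.33 |
| Hydralazine follow-up, three times daily | 10 mg | 100 mg | 10-20-40-80-160 | 160/100 = 1.60 |
| Hydralazine item 3b, three times daily | 25 mg | 100 mg | 25-50-100 | 1.00 |

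**Where it goes over.** At verapamil SR 240 mg the drug is not at 360 mg, so the next proposal is 480 mg. At hydralazine 80 mg three times daily the drug is not at 100 mg, so the next proposal is 160 mg.

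**Timing from each drug's own start.** Verapamil SR needs 2 doublings, 2 x (2 to 4) = 4 to 8 weeks. Hydralazine needs 4 doublings, 4 x (2 to 4) = 8 to 16 weeks. Both assume that blood pressure is above goal at every visit, that the heart-rate check does not divert the patient to the provider, and that the provider signs each earlier step unchanged.

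**Conflict within the hydralazine protocol.** Item 3b takes 10 mg to 25 mg, then 50 and 100 mg, which ends on the maximum. But a patient newly started on 10 mg under item 3b is sent to the follow-up item, and that loops back to itself. There 10 mg goes to 20 mg. The conflict is on the ordinary path for a new starter.

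**Patients who enter on another dose.** Doubling exceeds the maximum whenever M/2 < d < M. This applies to every doubling line: ACEi/ARB PROTOCOL item 3, BETA-BLOCKER PROTOCOL item 4, both calcium channel blocker lines, and both hydralazine lines. Purely as illustrations, lisinopril 30 mg would go to 60 mg against 40 mg, and hydralazine 75 mg to 150 mg three times daily against 100 mg. The documents give no such entry doses.

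**After a cap.** With next dose = min(2d, M), verapamil SR runs 120-240-360 mg. With the cap and the 10-to-25 mg step, the hydralazine follow-up runs 10-25-50-100 mg three times daily. Both end on the stated maximum.

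**The case against.** The best reply is that the ceiling is already there. A maximum dose means a cap, it is printed in the step that sends the nurse to these protocols, and the doubling lines refer back to it. Going over needs a reader who checks the maximum and then proposes more than it.

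That is a fair account of what a careful nurse would do, but it does not complete the instruction. At verapamil SR 240 mg the drug is not at maximum, so the exit to the next drug is closed, and the only other instruction is to double. If the ceiling forbids doubling, nothing is left to follow. Hydralazine 80 mg three times daily has the same gap. The conflict between 20 mg and 25 mg remains on either reading.

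The second reply is that safeguards are strong, and this stands. The provider selects and orders the drug and dose. The nurse works with a PA or NP at the same site, who may suggest deviations. Adverse effects are assessed at every visit, and new ones go to the provider. The medication steps are to be discussed with the provider. Hydralazine is reached only after maximum tolerated doses of three other classes. These points keep the matter small.

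A reader might infer that participants will be given doses above the limits. The documents do not support that: what exceeds the limit is a draft order that a prescriber must still accept or change. A reader might also infer that the defect is confined to the calcium channel blocker and hydralazine lines. From the stated starting doses it is, but the ACEi/ARB and beta-blocker lines are equally uncapped for a patient who enters between half the maximum and the maximum.

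**Conclusion.** The point holds as a minor safety correction. On a literal reading from the stated starting doses, two loops propose doses above the appendix's own maxima: by 33% for verapamil SR at the second doubling, and by 60% for hydralazine at the fourth. The hydralazine follow-up also disagrees with item 3b. The absence of a cap is general, but for the other drugs it matters only for entry doses that the documents do not give.

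The conclusion rests on the printed doses and on reading the doubling lines as they stand. The documents do not say how many patients would reach these steps, or whether the SmartSet orders cap the dose. Nothing here touches the sample size in section 11.2, the power or the planned analysis, and no inference about bias in the hospitalization comparison follows.

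**What to change.** Make two changes to Appendix I.

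1. Add one general rule covering every doubling line in the ACEi/ARB, beta-blocker, calcium channel blocker and hydralazine protocols: *any doubled dose is not to exceed the stated maximum dose*.
2. In the hydralazine follow-up, carry over the step from item 3b: *if taking 10 mg three times daily, propose 25 mg three times daily; otherwise double the current dose, not to exceed the stated maximum dose*.

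The schedules for lisinopril, losartan, carvedilol and amlodipine from their stated starts do not change. Any SmartSet that copies these rules should be updated to match.

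The cost is a few lines of text and any matching order-set edit. The appendix is reviewed every year, so the change can be made then. Section 14.2 requires submission to all the IRBs (UTSW, THR and VA North Texas) and their approval before implementation. Data collection and analysis are unchanged.
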